8.4.4 Reporting to Industry Partners/External Collaborators

Selected nonserious and SAEs are also known as events of clinical interest (ECIs) and must be reported to Merck.

Events of clinical interest for this study include:

1. An overdose of pembrolizumab that is not associated with clinical symptoms or abnormal laboratory results. For purposes of this study, an overdose of pembrolizumab will be defined as any dose of 1,000 mg or greater (≥ 5 times the indicated dose). No specific information is available on the treatment of overdose of pembrolizumab. In the event of overdose, the participant should be observed closely for signs of toxicity. Appropriate supportive treatment should be provided if clinically indicated. If an adverse event(s) is associated with ("results from") the overdose of a Merck product, the adverse event(s) is reported as a serious adverse event, even if no other seriousness criteria are met.
2. An elevated AST or ALT lab value that is greater than or equal to 3X the upper limit of normal and an elevated total bilirubin lab value that is greater than or equal to 2X the upper limit of normal and, at the same time, an alkaline phosphatase lab value that is less than 2X the upper limit of normal, as determined by way of protocol-specified laboratory testing or unscheduled laboratory testing.*

*Note: These criteria are based upon available regulatory guidance documents. The purpose of the criteria is to specify a threshold of abnormal hepatic tests that may require an additional evaluation for an underlying etiology.

Additionally, any SAE brought to the attention of an investigator at any time outside of the time period specified above must be reported immediately to Merck if the event is considered drug related.

All initial and follow-up AEs, SAEs, and other reportable safety events will be recorded and reported to Merck within the time frames as indicated in Table 8.4.4.

Table 8.4.4 Reporting Time Periods and Time Frames for Adverse Events and Other Reportable Safety Events

Type of Event	Reporting Time Period: Consent to Randomization/ Allocation	Reporting Time Period: Randomization/ Allocation through Protocol-specified Follow-up Period	Reporting Time Period: After the Protocol-specified Follow-up Period	Time Frame to Report Event and Follow-up Information to Merck:
Serious Adverse Event (SAE) including Cancer and Overdose	Report if: - due to protocol-specified intervention - causes exclusion - participant is receiving placebo run-in or other run-in treatment	Report all	Report if: - drug/vaccine-related. (Follow ongoing to outcome)	Within 2 business days but no longer than 3 calendar days of learning of event
Pregnancy/ Lactation Exposure	Report if: - due to intervention - causes exclusion	Report all	Previously reported – Follow to completion/termination; report outcome	Within 2 business days but no longer than 3 calendar days of learning of event
Event of Clinical Interest (require regulatory reporting)	Report if: - due to intervention - causes exclusion	Report - potential drug-induced liver injury (DILI) - require regulatory reporting	Not required	Within 2 business days but no longer than 3 calendar days of learning of event

SAE reports and any other relevant safety information are to be forwarded to the Merck Global Safety facsimile number: [REDACTED]

A copy of all 15 Day Reports and Annual Progress Reports is submitted as required by FDA, European Union (EU), Pharmaceutical and Medical Devices Agency (PMDA), or other local regulators. Investigators will cross-reference this submission according to local regulations to the Merck Investigational Compound Number (IND, CSA, etc.) at the time of submission. Additionally, investigators will submit a copy of these reports to Merck & Co., Inc. (Attn: Worldwide Product Safety, [REDACTED]) at the time of submission to FDA.

8.5 Follow-up of Adverse Events

All participants who experience adverse events will be followed with appropriate medical management until resolved or stabilized, as determined by the investigator or until the initiation

of new anti-cancer therapy, whichever occurs first. For selected adverse events for which administration of the study drug/intervention was stopped, a re-challenge of the subject with the study drug/intervention may be conducted if considered both safe and ethical by the investigator.

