5.2 Dose Modifications and Dosing Delays

AEs associated with pembrolizumab exposure may represent an immunologic etiology. These immune-related AEs (irAEs) may occur shortly after the first dose or several months after the last dose of pembrolizumab treatment and may affect more than one body system simultaneously. Therefore, early recognition and initiation of treatment are critical to reducing complications. Based on existing clinical study data, most irAEs were reversible and could be managed with interruptions of pembrolizumab, administration of corticosteroids, and/or other supportive care. For suspected irAEs, ensure adequate evaluation to confirm etiology or exclude other causes. Additional procedures or tests such as bronchoscopy, endoscopy, skin biopsy may be included as part of the evaluation. Dose modification and toxicity management guidelines for irAEs associated with pembrolizumab are provided in Table 5.2-1. Additional guidelines for toxicity management for cytokine release syndrome and neurotoxicity are outlined in Sections 5.2.1 and 5.2.2 respectively.

Table 5.2-1 Dose modification and toxicity management guidelines for immune-related AEs associated with pembrolizumab

General instructions:

Severe and life-threatening irAEs should be treated with IV corticosteroids followed by oral steroids. Other immunosuppressive treatment should begin if the irAEs are not controlled by corticosteroids.

Pembrolizumab must be permanently discontinued if the irAE does not resolve or the corticosteroid dose is not ≤ 10 mg/day within 12 weeks of the last pembrolizumab treatment.

The corticosteroid taper should begin when the irAE is \leq Grade 1 and continue at least 4 weeks.

If pembrolizumab has been withheld, pembrolizumab may resume after the irAE decreased to \leq Grade 1 after corticosteroid taper.

irAEs	Toxicity grade (CTCAE V5.0)	Action with pembrolizumab	Corticosteroid and/or other therapies	Monitoring and follow-up
Pneumonitis	Grade 2	Withhold	Administer corticosteroids (initial dose of 1 – 2 mg/kg prednisone or equivalent) followed by taper Add prophylactic antibiotics for opportunistic infections	Monitor participants for signs and symptoms of pneumonitis Evaluate participants with suspected pneumonitis with radiographic imaging and initiate corticosteroid treatment
	Grade 3 or 4, or recurrent Grade 2	Permanently discontinue		

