Grade 2 Requires therapy or infusion interruption but responds promptly to symptomatic treatment (e.g., antihistamines, NSAIDs, narcotics, IV fluids); prophylactic medications indicated for ≤24 hrs.	Stop Infusion. Additional appropriate medical therapy may include but is not limited to: IV fluids Antihistamines NSAIDs Acetaminophen Narcotics Increase monitoring of vital signs as medically indicated until the participant is deemed medically stable in the opinion of the investigator. If symptoms resolve within 1 hour of stopping drug infusion, the infusion may be restarted at 50% of the original infusion rate (e.g., from 100 mL/hr to 50 mL/hr). Otherwise, dosing will be held until symptoms resolve and the participant should be premedicated for the next scheduled dose. Participants who develop Grade 2 toxicity despite adequate premedication should be permanently discontinued from further study drug intervention	Participant may be premedicated 1.5h (± 30 minutes) prior to infusion of pembrolizumab with: Diphenhydramine 50 mg po (or equivalent dose of antihistamine). Acetaminophen 500-1000 mg po (or equivalent dose of analgesic).
Grades 3 or 4 Grade 3: Prolonged (i.e., not rapidly responsive to symptomatic medication and/or brief interruption of infusion); recurrence of symptoms following initial improvement; hospitalization indicated for other clinical sequelae (e.g., renal impairment, pulmonary infiltrates) Grade 4:	Stop Infusion. Additional appropriate medical therapy may include but is not limited to: Epinephrine** IV fluids Antihistamines NSAIDs Acetaminophen Narcotics Oxygen Pressors Corticosteroids Increase monitoring of vital signs as medically indicated until the participant	No subsequent dosing

Life-threatening; pressor or ventilatory support indicated	
is deemed medically stable in the opinion of the investigator. Hospitalization may be indicated. **In cases of anaphylaxis, epinephrine should be used immediately. Participant is permanently discontinued from further study drug intervention.
	
Appropriate resuscitation equipment should be available at the bedside and a physician readily available during the period of drug administration. For further information, please refer to the Common Terminology Criteria for Adverse Events v5.0 (CTCAE) at http://ctep.cancer.gov		

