5.2.1 Dose modification for cytokine release syndrome (CRS)

For participants who develop cytokine release syndrome grades 1-3 after pembrolizumab, further doses of pembrolizumab will be held until CRS completely resolves. Once CRS has fully resolved, the clinical investigator may resume pembrolizumab 200 mg every 3 weeks. Pembrolizumab will be discontinued for participants who develop grade 4 CRS or any grade 3 CRS that does not resolve to Grade \leq 1 or baseline within 48 hours with tocilizumab therapy and/or best medical care.

Guidelines for the management of patients who develop CRS, including the use of tocilizumab, are outlined in Section 6.4.4.1.

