6.6 Participant Discontinuation Criteria

When a participant discontinues prior to trial completion, all applicable activities scheduled for the final trial visit should be performed at the time of discontinuation. Any adverse events which are present at the time of discontinuation should be followed in accordance with the safety requirements outlined in Section 8.3.

Discontinuation of study intervention does not represent withdrawal from the study.

Participants may discontinue study treatment at any time for any reason or be dropped from the study treatment at the discretion of the investigator should any untoward effect occur. In addition, a participant may be discontinued from study treatment by the investigator or the Sponsor if study treatment is inappropriate, the trial plan is violated, or for administrative and/or other safety reasons. Specific details regarding procedures to be performed at study treatment discontinuation are provided in the subsequent sections.

A participant may be discontinued from study treatment but continue to be monitored in the study for any of the following reasons:

- The participant or participant's legally acceptable representative requests to discontinue study treatment.
- Any progression or recurrence of any malignancy, or any occurrence of another malignancy that requires active treatment.
- Unacceptable adverse experiences/dose-limiting toxicities including:
 - Grade 3 or higher immune-related AE that warrant discontinuation as outlined in Table 5.2-1

- Grade 3 or higher infusion reaction as outlined in Table 5.2-2
- Grade ≥ 3 CRS not responsive to tocilizumab therapy and/or best medical care after 72 hours or grade 4 CRS
- Grade ≥ 3 ICANS not responsive to best medical care after 72 hours or grade 4 ICANS
- Recurrent grade 2 pneumonitis
- The participant has a medical condition or personal circumstance which, in the opinion of the investigator and/or sponsor, placed the participant at unnecessary risk from continued administration of study treatment.
- The participant has a confirmed positive serum pregnancy test
- Noncompliance with study treatment or procedure requirements
- The participant is lost to follow-up
- Completion of 35 treatments (approximately 2 years) with pembrolizumab
- Administrative reasons

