6.8 Participant Replacement Strategy

If a participant is enrolled but does not receive any doses of pembrolizumab, the participant may be replaced.

If a participant is enrolled and receives less than 4 cycles of therapy and discontinues therapy or withdraws from the study for reasons other than disease progression, the participant will not be evaluated for the primary efficacy endpoint and will be replaced. However, all participants who receive at least one dose of pembrolizumab will be included in the safety analysis for adverse events (including those that received < 4 cycles of therapy).

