Appendix 3 Contraceptive Guidance and Pregnancy Testing

Contraception

Pembrolizumab may have adverse effects on a fetus in utero. Refer to below for approved methods of contraception.

For this study, male participants will be considered to be of non-reproductive potential if they have azoospermia (whether due to having had a vasectomy or due to an underlying medical condition).

Pregnancy

If a participant inadvertently becomes pregnant while on treatment with pembrolizumab, the participant will be immediately discontinued from study intervention(s). The site will contact the participant at least monthly and document the participant's status until the pregnancy has been completed or terminated. The outcome of the pregnancy will be reported to Merck within 2 working days if the outcome is a serious adverse experience (e.g. death, abortion, congenital anomaly, or other disabling or life-threatening complication to the mother or newborn). The study Investigator will make every effort to obtain permission to follow the outcome of the pregnancy and report the condition of the fetus or newborn to Merck.

If a male participant impregnates his female partner, the study personnel at the site must be informed immediately and the pregnancy must be reported to Merck and followed as described in Section 8.7.

Breastfeeding

It is unknown whether pembrolizumab is excreted in human milk. Since many drugs are excreted in human milk, and because of the potential for serious adverse reactions in the nursing infant, participants who are breastfeeding are not eligible for enrollment.

Woman of Childbearing Potential (WOCBP)

A woman is considered fertile following menarche and until becoming post-menopausal unless permanently sterile (see below)

Women in the following categories are not considered WOCBP:

- Premenarchal
- Premenopausal female with 1 of the following:
 - Documented hysterectomy
 - Documented bilateral salpingectomy
 - Documented bilateral oophorectomy

Note: Documentation can come from the site personnel's review of the participant's medical records, medical examination, or medical history interview.

- Postmenopausal female
 - A postmenopausal state is defined as no menses for 12 months without an alternative medical cause.
- A high follicle-stimulating hormone (FSH) level in the postmenopausal range may be used to confirm a postmenopausal state in women not using hormonal contraception

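### Section 8.5 permits re-challenge without excluding the events that Tables 5.2-1 and 5.2-2 make permanent stops, and section 6.6 words as optional some stops that are mandatory elsewhere

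*Combined protocol and SAP*

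**What the plan says.** Section 8.5 deals with following adverse events to resolution. For events that it calls selected, once the drug has been stopped, it adds that "a re-challenge of the subject with the study drug/intervention may be conducted if considered both safe and ethical by the investigator". It does not say which events are selected and does not mention section 5.2.

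Section 5.2 sets the disposition by event and grade. The general instructions to Table 5.2-1 state: "Pembrolizumab must be permanently discontinued if the irAE does not resolve", or if the steroid dose cannot be brought down in time. The body of that table requires permanent discontinuation for, among others, Grade 3-4 or recurrent Grade 2 pneumonitis, Grade 3-4 nephritis and Grade 3-4 myocarditis. For Grade 3-4 infusion reactions, Table 5.2-2 says: "Participant is permanently discontinued from further study drug intervention". Section 5.2.1 says: "Pembrolizumab will be discontinued for participants who develop grade 4 CRS", and section 5.2.2 uses the same form for Grade 4 ICANS.

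Section 6.6 introduces its list with: "A participant may be discontinued from study treatment but continue to be monitored in the study for any of the following reasons". The list includes Grade 3 or higher infusion reactions, Grade 4 CRS, Grade 4 ICANS, recurrent Grade 2 pneumonitis and a confirmed positive pregnancy test. Appendix 3, in contrast, makes stopping for pregnancy immediate and obligatory.

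**The concern.** There are two mismatches. First, section 8.5 leaves re-dosing after a stop to the investigator, while the two tables in section 5.2 close off re-dosing for named events. Second, section 6.6 uses a permissive verb for stops that other sections state as requirements.

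The main stake is safety: what happens to a participant after a severe toxicity could depend on which section the site reads.

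The secondary stake is in the data. Under sections 3.2 and 6.8, when a participant stops before four cycles for a reason other than progression, "the participant will not be evaluated for the primary efficacy endpoint and will be replaced". A participant with the same toxicity who is re-dosed and completes four cycles is evaluable under sections 7.1 and 9.3.1. The section 2.3 count of discontinuations for toxicity could also differ according to which section was followed.

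**Working it through.** The plan gives no figure on this point, so the check sets the passages side by side.

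| Event | Section 5.2 or Appendix 3 | Section 6.6 | Section 8.5 |
|---|---|---|---|
| Grade 3-4 infusion reaction | Permanent stop (Table 5.2-2) | Under *may*; points to Table 5.2-2 | Not excluded |
| Grade 3-4 pneumonitis, nephritis or myocarditis | Permanent stop (Table 5.2-1) | Under *may*; points to Table 5.2-1 | Not excluded |
| Recurrent Grade 2 pneumonitis | Permanent stop (Table 5.2-1) | Under *may*; no cross-reference | Not excluded |
| Grade 4 CRS or ICANS | Mandatory stop, not called permanent (5.2.1, 5.2.2) | Under *may*; no cross-reference | Not excluded |
| Pregnancy | Mandatory and immediate, not called permanent (Appendix 3) | Under *may*; no cross-reference | Out of reach: 8.7 says pregnancy is not an adverse event |

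1. *Does section 8.5 reach the permanent stops?* Its scope is "For selected adverse events for which administration of the study drug/intervention was stopped, a re-challenge of the subject with the study drug/intervention may be conducted". Nothing there limits it to temporary interruptions. Section 5.2 already has its own rules for those, using the words withheld and resume and tied to the grade to which the event has resolved. Section 8.5 uses different words (stopped, re-challenge) and a different test (the investigator's view of safety and ethics). If it covered only the withheld events, it would add little to section 5.2. The permanent-stop events are therefore not excluded on the text.

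2. *Is the verb in section 6.6 about stopping or about monitoring?* The sentence carries both, and either reading is available. Section 6.7, which follows directly, uses *must* for withdrawal of consent and *may* for its other reasons. A reader has grounds to think that the protocol distinguishes the two verbs.

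3. *Which section governs?* No statement of precedence was found.

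4. *Can the endpoint effect be sized?* For evaluability to change, a participant must (a) meet a mandatory-stop criterion before completing four cycles, (b) be dosed again despite section 5.2, and (c) go on to complete four cycles. The documents give no rate for any of these. Section 9.2 expects severe events in 15-20% irrespective of cause: 0.15 × 25 = 3.75 and 0.20 × 25 = 5, so about 4 to 5 participants. Only an unstated part of these would meet (a) to (c) together.

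5. *Does the wording touch the design calculation?* No. Exact binomial enumeration of the design in section 9.1.1 (stop at 0 or 1 response in 15; reject at 6 or more in 25) gives type I error 0.033 and early stopping 0.549 at a response rate of 10%, and power 0.802 at 30%. These agree with the stated 5% limit, 55% and 80%, and none depends on this wording.

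**The case against.** The strongest reply is that the sections can be read together. Section 8.5 is a general follow-up paragraph, limited to selected events and phrased as a permission. Section 5.2 supplies many reversible stops for it to describe: withheld immune events, endocrinopathies, resolved Grade 1-3 CRS or ICANS, and interrupted Grade 2 infusion reactions. Nothing in section 8.5 claims to override a specific permanent-stop entry.

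In section 6.6, *may* can be taken as permission to keep monitoring after a stop. The preceding text says that stopping treatment is not withdrawal, and the list includes loss to follow-up and completion of 35 treatments, where discretion over stopping makes little sense. The immune-event and infusion items refer back to the section 5.2 tables. Sections 3.1, 3.6 and 5.1 also end treatment at dose-limiting toxicity or unacceptable adverse events.

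Much of this stands. These readings are reasonable, and the cross-references weaken the section 6.6 argument for immune events and infusion reactions. They are not compelled, however. *Selected* is undefined, section 8.5 has no link to section 5.2, and the section 6.6 items for CRS, ICANS, recurrent Grade 2 pneumonitis and pregnancy carry no cross-reference. A safety rule should not depend on the site choosing the harmonising interpretation.

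**Conclusion.** The point holds in a limited form. It concerns one sentence in section 8.5 that does not exclude the permanent stops in Tables 5.2-1 and 5.2-2, and four items in section 6.6 (CRS, ICANS, recurrent Grade 2 pneumonitis, pregnancy) worded as optional where other sections are mandatory. It rests on the text alone.

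A reader might infer more, in three ways that the documents do not support.

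- *That section 5.2 and Appendix 3 make every such stop permanent and mandatory.* Some Table 5.2-1 entries are withhold-and-resume or discretionary (footnotes d and e), and neither the CRS and ICANS text nor Appendix 3 uses the word permanent.
- *That section 8.5 allows re-challenge in pregnancy.* Section 8.7 says that pregnancy is not an adverse event, so only the wording of section 6.6 against Appendix 3 conflicts.
- *That the trial's efficacy conclusion is materially at risk.* How often a trial finishes close to the cut-off of 6 responses does not measure what this wording does. The effect needs the chain of events in step 4 above, for which there are no rates. An effect on evaluability or on the toxicity-discontinuation count is possible, probably small, and not quantifiable here.

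**What to change.** Reconcile sections 8.5 and 6.6 with section 5.2 and Appendix 3 so that each listed event has one stated disposition wherever it appears:

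- In section 8.5, define the selected events or refer to section 5.2, and state whether re-challenge can apply to any event that section 5.2 calls a permanent discontinuation.
- In section 6.6, bring the verb into line with section 5.2 and Appendix 3 for CRS, ICANS, recurrent Grade 2 pneumonitis and pregnancy, and separate permission to continue monitoring from the rule on stopping.

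The clinical team decides which rule stands; none is proposed here. The different time limits for unresolved Grade 3 CRS or ICANS (48 hours in sections 5.2.1, 5.2.2 and 9.2; 72 hours in section 6.6) are a separate discrepancy that could be reconciled in the same amendment.

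No new counting rule is needed in section 9.3. Counting re-dosed participants as discontinuations would change what that endpoint means.

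The cost is a wording amendment with its usual approvals. It adds no patients, procedures or analyses.
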